The patient will be positioned supine, with the ipsilateral thigh and knee prepped in sterile fashion using chlorhexidine/alcohol. A high-frequency ultrasound probe will be covered in a sterile transparent dressing. First a survey scan will be performed at the anteromedial aspect of the mid-thigh, defined as the middle one-third of the distance between the base of the patella and the lower border of the greater trochanter. The probe will be oriented transversely to identify the femoral artery and saphenous nerve in short-axis cross-section, and an image will be recorded. The adductor canal will be scanned in its entirety, with special consideration paid to the femoral triangle just caudad to the inguinal ligament and the popliteal fossa; images will be recorded at both locations. An in-line injection pressure manometer, the Compass CT (Centurion Medical Products, Williamston, MI), will be used to measure injection pressure during adductor canal nerve blocks. A 4 inch, blunt, short beveled needle will be introduced in-plane, in an anterolateral to posteromedial direction, close to the fascial plane between the sartorius and vastus medialis muscles. After negative aspiration, the needle tip location will be confirmed by injection of 0.5 mL of air. Subsequently, an initial bolus of 1 mL of local anesthetic will be administered at < 15 psi in order to decrease risk of intraneurial injection and nerve injury. The remaining 14 mL of ropivacaine 0.5% will thereafter be injected in 5 mL aliquots, maintaining either > 20 psi or < 15 psi based on patient randomization. Injectate spread will be assessed by ultrasound survey after completion of the adductor canal nerve block, where injectate spread is defined as the distance between the uppermost and lowermost limits of spread of local anesthetic as assessed by ultrasound.

Block evaluation will occur 30 minutes after block placement, with motor and sensory testing of both lower extremities as previously mentioned. Additionally, NRS pain ratings will be recorded pre- and post-evaluation. Block success will be determined by testing for pinprick sensation in the saphenous nerve distribution in the ipsilateral lower leg as compared with the contralateral lower leg. Patients who fail to demonstrate block success will be withdrawn from further study.

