Of note, all operative and post-operative procedures are standard of care for subjects undergoing elective anterior cruciate ligament repair in the distal lower extremity, except for the purposeful application of an injection pressure > 20 psi during an adductor canal block. The standard of care for adductor canal block is the injection of local anesthetic easily, without having to overcome high resistance. The reason for this is to avoid intrafascicular injection, which is thought to be associated with nerve injury. Usually, this translates to injection at a low pressure. However, if the injection can be proved not to be against high resistance, then a high injection pressure would be no different from a low injection pressure with regards to the risk of intrafascicular injection and nerve injury. Both injection pressure groups in this study include the provision of an initial 1 mL bolus of injection to rule out intrafascicular injection, and therefore to minimize the risk of nerve injury. Thus, despite the deviation from the standard of care in the high injection pressure group, there is no additional risk for any complications related to the high injection pressure.

9) Data Management*

Power analysis using a 2-sided type I error protection of .05 and a power of 80% yields a minimum of 20 patients in each group to detect a reduction in incidence of motor weakness of 30% with normal pressure (<15 psi) vs. high pressure (>20 psi). We plan to enroll 25 patients in each group to account for possible unanticipated patient dropout.

Study data will be stored in the UMH office of Anesthesiology, Perioperative Medicine & Pain Management, located at [name]. Study files will be locked and accessible only to the study team, in order to prevent any breach of confidentiality.

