The study investigators and their staff will have access the research subjects' medical records and associated information as may be necessary for purposes of this study. These records and results will not be identified as pertaining to the research subject in any publication without subjects' expressed permission. The Investigator, collaborators and staff will consider these records confidential to the extent permitted by law. The Food and Drug Administration (FDA), Department of Health and Human Services (DHHS) and the patients' health care providers, including authorized University or Hospital staff not involved in the study may review these research records. The records may also be reviewed for audit purposes by authorized University of Miami employees or other agents who will be bound by the same provisions of confidentiality.

10) Provisions to Monitor the Data to Ensure the Safety of Subjects*

During the procedure, the patients will be monitored in accordance with the standard of care. Should research subjects exhibit any signs of toxicity or other complication from the procedure,

they will be cared for in the standard manner as they would be if not enrolled in the study—cessation of the procedure and a systematic evaluation for any possible treatment.

An extra precautionary step during the procedure will be taken to minimize any risk of nerve injury associated with high pressure injection. This is the injection of 1 mL of local anesthetic at a low pressure to rule out intrafascicular injection, which is thought to cause nerve injury. This precautionary step will be taken in both the low injection pressure and high injection pressure groups, such that the risk of nerve injury as a result of procedure is both minimized and equalized between both groups.

Outside of standard monitoring and the extra precautionary step, patients will not receive any further monitoring for safety concerns. There are no other study-related safety concerns.

11) **Withdrawal of Subjects***

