Research subjects will be counseled that their participation in the study is voluntary, and that they may refuse to participate or withdraw from the study at any time without penalty or loss of benefits to which the patients are otherwise entitled. Withdrawal from the study will not affect their medical care they receive from the study doctor or from the University of Miami Hospital. The patient will be counseled that they must tell their study doctor if they wish to stop taking part in the study.

Furthermore, the research subjects' participation in the study may be discontinued without their consent at any time by the study doctor, for instance if the patient has a medical condition which is a contraindication for the procedure, or if a serious, potentially life-threatening complication develops as a result of the procedure. The IRB or regulatory authorities may also discontinue research subjects' participation in the study.

In the case that research subjects are withdrawn from the study, the study staff and the investigator will stop collecting health information; however, they will continue to use the information already collected to evaluate the study results.

Finally, if research subjects start the study and then decide to withdraw, they cannot later continue to participate in the study.

12) **Risks to Subjects***

There are risks normally associated with adductor canal nerve block. These risks are listed below:

UNCOMMON	RARE
Failure of the nerve block to work properly.	Injury to the blocked nerve.
	Excessive bleeding at the site of injection.
	Infection at the site of injection.

	Inadvertent injection of local anesthetics into the bloodstream, causing seizures and/or heart rhythm problems.
--	---

In patients receiving an injection pressure > 20 psi, there is an increased risk of injury to the blocked nerve, such as with intrafascicular injection. To minimize this risk, all injections will be preceded by injection of 1 mL of local anesthetic at an injection pressure < 15 psi, to rule out intrafascicular injection.

13) Potential Benefits to Subjects*

There is no direct benefit to the subjects.

14) Sharing of Results with Subjects*

Results will not be shared with research subjects or their physicians.

15) Setting

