Potential research subjects will be recruited for the research study on the day of surgery at the UMH and The Lennar Foundation Medical Center ambulatory surgery suite. They will be evaluated prior to surgery in the preoperative holding area and if all inclusion criteria are fulfilled and all exclusion criteria absent, the informed consent process will begin. The risks and benefits of participating in the research study will be discussed at length with the potential subject and a comprehensive informed consent form will be reviewed. Potential subjects will be advised that they may refuse to take part in the study at any time without any adverse consequences on their medical care. They will be informed that they will not receive any direct benefit from the study, nor will they receive any compensation for participation.

18) Local Number of Subjects

50 subjects will be recruited into this study—25 in each group.

19) Provisions to Protect the Privacy Interests of Subjects

The study investigators and their staff will have access to the research subjects' medical records and associated information as may be necessary for purposes of this study. These records and results will not be identified as pertaining to the research subject in any publication without subjects' expressed permission. The Investigator, collaborators and staff will consider these records confidential to the extent permitted by law. The Food and Drug Administration (FDA), Department of Health and Human Services (DHHS) and the patients' health care providers, including authorized University or Hospital staff not involved in the study may review these research records. The records may also be reviewed for audit purposes by authorized University of Miami employees or other agents who will be bound by the same provisions of confidentiality.

A description of this clinical trial will be available on <http://www.ClinicalTrials.gov>, as required by U.S. Law. This Web site will not include information that can identify the research subjects. At most, the Web site will include a summary of the results.

20) Compensation for Research-Related Injury

The research subjects will undergo a procedure which is already considered a standard of care for the surgery at hand, with regards to pain control. The only modification to this is that one group will receive a high pressure injection which may be associated with an increased risk for nerve injury.

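### The protocol says both that high injection pressure adds no risk and that it increases nerve-injury risk; it plans no nerve-injury outcome, and collection stops in block failures already exposed

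*Combined protocol and SAP*

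**What the plan says.** **Risk statements.** Section 8 (Procedures Involved) identifies injection above 20 psi as the one departure from standard of care. It argues that "if the injection can be proved not to be against high resistance, then a high injection pressure would be no different" in its risk of intrafascicular injection and nerve injury. It then points to the "initial 1 mL bolus of injection to rule out intrafascicular injection, and therefore to minimize the risk of nerve injury" given in both groups, and concludes that "there is no additional risk for any complications related to the high injection pressure". Section 10 says that, because of the same bolus, "the risk of nerve injury as a result of procedure is both minimized and equalized between both groups". Section 12 (Risks to Subjects) says that above 20 psi "there is an increased risk of injury to the blocked nerve, such as with intrafascicular injection", and offers the bolus "at an injection pressure < 15 psi, to rule out intrafascicular injection" as the way to minimize this. Section 20 says that "one group will receive a high pressure injection which may be associated with an increased risk for nerve injury".

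**Outcomes and follow-up.** The endpoints in sections 1, 2 and 7 do not include nerve injury. Section 10 plans no safety monitoring beyond standard monitoring and the bolus. Section 8 provides a baseline bilateral sensory and motor examination, a repeat 30 minutes after the block, and four postoperative examinations by a blinded team, the last at discharge. After that, the contacts described are the LEFS at the initial physical therapy assessment and then weekly for 4 weeks (section 8), by telephone (section 15).

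**Withdrawal.** Section 8 withdraws patients whose block has not succeeded at the 30-minute evaluation. Under section 11, collection of health information stops for withdrawn patients, while data already held are still used.

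**The concern.** The protocol takes different positions on the risk of the one procedure it says departs from standard of care. A consent form that followed either position would disagree with part of the protocol.

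The follow-up adds to the problem. The block is meant to give postoperative analgesia, so a deficit found before discharge may simply be the block working; the protocol gives no block duration. A deficit that appears or persists afterwards would be more informative, but it has no defined place to be recorded by arm. It would surface only if a patient volunteered it or it happened to be in the medical record. For block failures, who also received the assigned pressure, study collection has already ended.

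**Working it through.** The protocol gives no nerve-injury rate, so it has no figure of its own to reproduce on this point. Its sample-size statement concerns motor weakness and does not bear on the question. The check is mainly a comparison of text.

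**1. The risk statements side by side**

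| Section | Position on high pressure | Is the bolus mentioned? |
|---|---|---|
| 8 | No added risk of any complication | Yes, as the reason |
| 10 | Nerve-injury risk equalized | Yes, as the reason |
| 12 | Nerve-injury risk increased | Yes, to minimize it |
| 20 | Nerve-injury risk may be increased | No |

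Sections 8, 10 and 12 rely on the same bolus. Two of them conclude that the arms are equal; the third says only that the risk is minimized. The bolus is identical in both arms, and the arms differ only afterwards. It therefore equalizes risk only if it fully removes whatever risk high pressure would add, and section 12 does not claim that.

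**2. Premise and conclusion in section 8.** The argument concerns intrafascicular injection and nerve injury. The conclusion covers every complication of high pressure, which is wider than the argument supports.

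**3. Where a late deficit could be recorded.** There are four postoperative examinations, all by discharge, then 1 + 4 = 5 LEFS administrations. No neurological item is described for any of the five. Sections 9 and 19 allow access to medical records, but no review for nerve injury is planned.

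**4. Exposed patients who leave follow-up.** Block failure is listed as uncommon in section 12, with no rate. Assume 1 to 3 failures per arm (1/25 = 4% to 3/25 = 12%):

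- exposed patients withdrawn: 2 × 1 = 2 to 2 × 3 = 6;
- weekly calls not made to them: 2 × 4 = 8 to 6 × 4 = 24.

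**5. What recording symptoms could show.** With zero events in n patients, the exact two-sided 95% upper limit is 1 − 0.025^(1/n):

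- n = 25: 13.7%;
- n = 24: 14.2%;
- n = 22: 15.4%.

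For 0/25 against 0/25, the Newcombe 95% interval for the difference is −13.3 to +13.3 percentage points.

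Section 12 lists nerve injury as rare. At assumed true rates of 0.1% and 1%, the chance of at least one case among 25 is 1 − 0.999^25 = 2.5% and 1 − 0.99^25 = 22%.

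**The case against.** The best defence is that section 12 describes risk before the bolus and sections 8 and 10 describe risk after it. Section 12 does move straight from the increased risk to the bolus, so this is a plausible intention and a reason to clarify the wording. But no section states the distinction, and section 20 gives a possible increase without mentioning the bolus.

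A reader might infer further contradictions that the text does not support:

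- **The bolus rules out the risk in some places and only lowers it in others.** No section says it rules out the risk. It is said to rule out intrafascicular injection and so to minimize nerve injury. Section 8's other phrase, "in order to decrease risk of intraneurial injection and nerve injury", fits that chain.
- **Section 8 drops its own condition.** It offers the bolus as what meets the condition. Whether the bolus is enough can be questioned, but the step is there.
- **There is no follow-up after discharge.** There is: a physical therapy assessment and weekly calls. What is missing is a nerve-injury item.
- **Data on a serious complication would be discarded.** Discontinuation on that ground is discretionary and data already collected are kept. Only later follow-up would be lost.

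It is also fair to say that a symptom question has limited yield. The operated limb is the blocked limb, so symptoms cannot be attributed to the block rather than to surgery, and 25 patients per arm give wide intervals. That stands, and it is why the question is offered as a low-cost addition and not as a test of safety.

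**Conclusion.** The point holds. The risk statements in sections 8 and 10 do not agree with those in sections 12 and 20, and section 8's conclusion is wider than its argument. No nerve-injury outcome is defined, and exposed block failures leave all study collection at 30 minutes without a safety exception. These findings rest on the text alone. The figure of 2 to 6 patients lost rests on an assumed failure rate of 4% to 12%.

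A reader might go further and conclude that high pressure is harmful, or that participants were misinformed. The documents support neither: they give no injury rate by pressure, and the consent form is not in the reviewed text. Nor could the trial show equal risk if symptoms were recorded, since zero events in both arms would still allow a difference of up to 13.3 percentage points either way. This is a matter of consistency and safety recording that should be corrected. It does not affect the ultrasound primary endpoint.

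**What to change.** 1. **Reconcile the risk statements** in sections 8, 10, 12 and 20, saying for each whether it refers to risk before or after the bolus, and bring section 8's conclusion into line with its argument. Check that the consent form carries the same position. This review does not say which position is right. Cost: wording and one document check.
2. **Amend section 11** so that patients withdrawn by the investigator, including for block failure, stay in safety follow-up subject to consent. These are new contacts: at most 4 weekly calls per withdrawn patient, or 8 to 24 calls under the 4% to 12% assumption.
3. **As a low-cost addition,** put one fixed question on new or persistent numbness or weakness in the blocked limb on the weekly LEFS calls. Report it by arm, descriptively, with exact intervals and no between-arm test, labelled as symptoms from any cause. With fix 2 included, this is at most 50 × 4 = 200 answers.

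The downsides are slightly longer calls, the extra calls to withdrawn patients, the need for a process to handle positive answers, symptoms that cannot be attributed to the block rather than surgery, and intervals too wide to show equal risk. No new visit or procedure is needed.

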NCT02563990

PROTOCOL TITLE:

INJECTION PRESSURE AND ADDUCTOR CANAL BLOCK

V2 7/10/2015

1) Protocol Title

Impact of Injection Pressure on the Spread of Local Anesthetic During Adductor Canal Nerve Block

Authors: [name], [name], [name], [name], DNP, [name], [name], [name], [name]
Department of Anesthesiology, University of Miami, Florida

Brief description: This is a prospective, randomized, single-blinded human clinical trial that will examine how injection pressure influences the spread of a given volume of injectate in the adductor canal, during adductor canal nerve block. Our study population will be patients undergoing elective anterior cruciate ligament repair in the distal lower extremity and receiving preoperative adductor canal nerve blocks for postoperative analgesia. They will be randomized into two groups of 25 patients each. We speculate that high injection pressures (>20 psi) will lead to greater spread of local anesthetic than low injection pressures (<15 psi) during mid-thigh adductor canal nerve blocks. Our primary endpoint is the spread of injectate, defined as the distance between the uppermost and lowermost limits of spread of local anesthetic as assessed by ultrasound. Our secondary endpoints are the incidence of femoral and sciatic nerve blocks 30 minutes after block placement, amount of IV opioid administered intraoperatively and postoperatively, postoperative pain (Numeric Rating Scale, 0-10), and postoperative physical therapy milestone achievement.

2) Objectives*

The purpose of this study is to evaluate the impact of injection pressure on the spread of local anesthetic in the adductor canal during an adductor canal nerve block. Our primary endpoint is the spread of injectate, defined as the distance between the uppermost and lowermost limits of spread of local anesthetic as assessed by ultrasound. Our secondary endpoints are the incidence of femoral and sciatic nerve blocks 30 minutes after block placement, amount of IV opioid administered intraoperatively and postoperatively, preoperative and postoperative pain (Numeric Rating Scale, 0-10), and postoperative physical therapy milestone achievement, namely Lower Extremity Function Scale (LEFS) scores.

3) Background*

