The adductor canal block of the saphenous nerve is a well-established regional anesthetic technique for knee surgery, and it is recognized for its excellent analgesia with a notable absence of motor involvement, even with continuous perineural local anesthetic infusions. The adductor canal block is known for a high success rate because the adductor canal can be easily visualized with ultrasound at the mid-thigh. While the anatomy of the adductor canal has been elucidated by several imaging and cadaveric studies, factors influencing the spread of local anesthetic during adductor canal nerve block are less well understood. Different volumes of local anesthetic injected

through myriad anatomic approaches produce variable spread. Injectate spread has been shown to span from the femoral triangle to the popliteal fossa with only 15 mL of aqueous volume. One case report notes the apparent partial blockade of the sciatic nerve as a result of a common transsartorial approach to the adductor canal block. Another case report notes motor block of the quadriceps muscle with a midthigh approach to the adductor canal block. Furthermore, one study reports a staggering 67% incidence of motor weakness associated with a bolus of 15 mL of local anesthetic through an adductor canal catheter placed in the midthigh. Additionally, injection pressure has been shown to dramatically influence the spread of lumbar plexus block. Sustained injection pressures > 20 psi during intermittent injection of local anesthetic into the lumbar plexus have been associated with a 60% incidence of bilateral femoral nerve block and a 50% incidence of neuraxial block to the level of T11 or above, compared to no spread in the low injection pressure group (< 15 psi). Injection pressure has not been studied in adductor canal nerve blocks in human clinical trials. We hypothesize that, for a given injectate volume, the pressure during injection will affect local anesthetic spread towards the femoral triangle (cranially) and the popliteal fossa

(caudally). We speculate that high injection pressures will lead to greater spread of local anesthetic during mid-thigh adductor canal nerve blocks.

4) Inclusion and Exclusion Criteria*

Inclusion criteria:

1. Planned general anesthetic.
2. ASA classes I, II, or III.
3. Patients aged 18-65.
4. English-speaking patients.

Exclusion criteria:

1. ASA classes IV and V.
2. Patients younger than 18 or older than 65.

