3. Contraindication to regional anesthesia (coagulopathy, patient refusal).
4. Allergy to local anesthetic or other study medications.
5. $BMI > 35 \text{ kg/m}^2$.
6. Chronic opioid use (daily or almost daily use for > 3 months).
7. Active illicit drug use.
8. Additional surgical site other than the limb for adductor canal block.
9. Pregnancy.
10. Preexisting neuropathy in the operative limb.
11. Inability to communicate to investigators or hospital staff.
12. Inability to speak or understand English.

5) Number of Subjects*

50 subjects will be recruited into this study—25 in each group.

6) Study-Wide Recruitment Methods*

Potential research subjects will be recruited for the research study on the day of surgery at the University of Miami ambulatory surgery suite. The study team will have access to the operating room surgical schedule and will identify any patients scheduled for an elective anterior cruciate ligament repair in the distal lower extremity. These patients will be evaluated on the day of surgery in the preoperative holding area and the preoperative history and physical will be reviewed. If all inclusion criteria are fulfilled and all exclusion criteria absent, the informed consent process will begin. The risks and benefits of participating in the research study will be discussed at length with the potential subject and a comprehensive informed consent form will be reviewed. Potential subjects will be advised that they may refuse to take part in the study at any time without any

adverse consequences on their medical care. They will be informed that they will not receive any direct benefit from the study, nor will they receive any compensation for participation.

7) Study Endpoints*

Our primary endpoint is the spread of injectate, defined as the distance between the uppermost and lowermost limits of spread of local anesthetic as assessed by ultrasound. Our secondary endpoints are the incidence of femoral and sciatic nerve blocks 30 minutes after block placement, amount of IV opioid administered intraoperatively and postoperatively, preoperative and postoperative pain scores (Numeric Rating Scale, 0-10), and postoperative physical therapy milestone achievement.

8) Procedures Involved*

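### Section 9 powers the trial for motor weakness, so its 80% power and 20 per group do not apply to the primary endpoint, ultrasound spread distance

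*Combined protocol and SAP*

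**What the plan says.** Section 2 (Objectives) sets the aim: "The purpose of this study is to evaluate the impact of injection pressure on the spread of local anesthetic in the adductor canal". Section 3 (Background) gives the hypothesis in the same terms: "We speculate that high injection pressures will lead to greater spread of local anesthetic during mid-thigh adductor canal nerve blocks". Section 7 (Study Endpoints) follows through: "Our primary endpoint is the spread of injectate, defined as the distance between the uppermost and lowermost limits of spread". Section 8 (Procedures Involved) repeats that definition and fixes the timing: "Injectate spread will be assessed by ultrasound survey after completion of the adductor canal nerve block".

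Section 9 (Data Management) holds the only sample-size reasoning. With two-sided alpha 0.05 and 80% power it arrives at "a minimum of 20 patients in each group to detect a reduction in incidence of motor weakness of 30" percent, comparing pressure below 15 psi with pressure above 20 psi. It then raises enrolment to 25 per group for dropout, without giving a dropout rate.

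Motor weakness is not named in any endpoint list. The nearest item is in section 7: "Our secondary endpoints are the incidence of femoral and sciatic nerve blocks 30 minutes after block placement". Section 8 schedules the matching assessment: "Block evaluation will occur 30 minutes after block placement, with motor and sensory testing of both lower extremities as previously mentioned".

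**The concern.** The outcome that sizes the trial is a proportion; the outcome that answers its question is a distance. Power for one does not carry over to the other. The first depends on two incidences, the second on a mean difference and an SD, and the protocol gives neither of the latter. A reader therefore cannot tell what difference in spread 50 patients could detect. If the spread comparison turns out null, nothing in the plan helps to separate no relevant effect from too few patients.

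There is a second, smaller gap. Even for motor weakness, the 80% depends on quantities that section 9 leaves out, so the calculation that was done cannot be checked.

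**Working it through.** **Inputs from the protocol.** Two-sided alpha 0.05, power 80%, a nominal 30% reduction in motor weakness, a minimum of 20 per group and 25 enrolled per group (all section 9; the 25 also in section 5). Not given: base rate, absolute or relative, test and dropout rate for motor weakness; SD, relevant difference and test for spread.

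**Step 1. Can 20 per group be reproduced?** Take 30% as 30 points and try 30% versus 0%, with (1.960 + 0.842)² = 7.849.

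- Unpooled: n = 7.849 × [0.30 × 0.70 + 0 × 1] / 0.30² = 7.849 × 0.21 / 0.09 = 18.3.
- Pooled, mean rate 0.15: n = [1.960 × √(2 × 0.15 × 0.85) + 0.842 × √0.21]² / 0.09 = 21.0 (21.02 before rounding up).

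These round up to 19 and 22, so 20 lies between two common formulas at that pair of rates. Away from it the requirement climbs: the pooled formula gives 32 per group at 40% versus 10% and 43 at 67% versus 37%. If 30% is relative, the pooled formula gives 95 per group for 67% versus 46.9%, and comes down to 22 only at 100% versus 70%, the mirror of 30% versus 0%.

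**Step 2. Power for motor weakness at the planned sizes.** Exact enumeration of both binomials for a 30-point difference, with the test assumed:

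| High vs low pressure | Chi-square, 20 | Chi-square, 25 | Fisher, 20 | Fisher, 25 |
|---|---|---|---|---|
| 30% vs 0% | 89% | 97% | 76% | 81% |
| 40% vs 10% | 62% | 73% | 49% | 59% |
| 67% vs 37% | 45% | 62% | 34% | 51% |

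Chi-square here is without continuity correction. With 20 per group it falls to 81% at 32% versus 2%, and Fisher's test does not reach 80% for any 30-point pair.

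The last row is an illustration only. Section 3 points both ways on the base rate. It describes the block as "recognized for its excellent analgesia with a notable absence of motor involvement", but also cites a study with 67% motor weakness after 15 mL given through a catheter. Section 9 is tied to neither statement.

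**Step 3. What can 50 patients detect in spread?** Assume a two-sample t-test at two-sided 0.05. Power comes from the noncentral t distribution with 2n − 2 degrees of freedom and noncentrality d × √(n/2), where d is the difference divided by the SD.

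- 25 per group: 80% power at d = 0.81 (0.809 × √12.5 = 2.86, 48 df).
- 20 per group: 80% power at d = 0.91 (0.909 × √10 = 2.87, 38 df).

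| True difference | Power, 20 per group | Power, 25 per group | n per group for 80% |
|---|---|---|---|
| 0.5 SD | 34% | 41% | 64 |
| 0.8 SD | 69% | 79% | 26 |
| 1.0 SD | 87% | 93% | 17 |

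In cm the detectable difference is d × SD. The protocol gives no SD; for assumed values of 2, 3, 4 and 5 cm it is 1.6, 2.4, 3.2 and 4.0 cm with 25 per group, and 1.8, 2.7, 3.6 and 4.5 cm with 20.

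**The case against.** Section 9 labels its 80% as power for motor weakness and never claims it for spread, so it makes no false statement. Nor is it empty: alpha, sidedness, power, a nominal effect and its direction are all given. Motor weakness is also not foreign to the trial. Section 8 tests femoral and sciatic motor function at 30 minutes, which is plausibly how the secondary block endpoint would be scored. All of this stands, and it limits the point. It does not repair it, because no other section justifies the sample size for the primary endpoint, and no section says that motor weakness is how the secondary endpoint is measured.

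Three stronger readings are tempting, and the documents support none of them.

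- A reader might infer that the trial is underpowered for spread. Without an SD or a relevant difference, that cannot be shown; 0.81 SD may or may not be small enough.
- A reader might infer that 20 per group is a miscalculation. It is attainable near 30% versus 0% or the mirror, so an error is not established. Equally, the figure cannot be declared correct, because the rates and the test behind it are not stated.
- A reader might take 67% as the intended base rate and conclude that the real power is 45%. The protocol cites that rate as background for a catheter technique and does not link it to section 9.

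**Conclusion.** The point holds and needs correcting before the sample size can be relied on. The sole power statement concerns a binary outcome that is not the primary endpoint, so the 80% and the 20 per group do not apply to the spread comparison. What is shown is that power for spread is unsupported, not that it is too low.

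Under an assumed t-test at two-sided 0.05, the planned 25 per group correspond to 80% power at 0.81 SD, or 0.91 SD with 20 evaluable. Whether that is adequate depends on two quantities that only the sponsor can supply. For motor weakness, the 20 per group is attainable only near 30% versus 0% or its mirror and is otherwise unverifiable. The missing items are specific: the base rate, absolute or relative, and the test.

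**What to change.** Keep 50 patients and restate section 9 in two parts.

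1. **Primary endpoint.** State that 25 per group give 80% power (two-sided 0.05, two-sample t-test) for a difference in spread of 0.81 SD, or 0.91 SD if only 20 per group are evaluable. Add the assumed SD and the relevant difference, both in cm. If the relevant difference is below 0.81 SD, state the lower power that results (for example 41% at 0.5 SD with 25 per group) and say that a null result would not exclude a relevant difference. Using 25 as the main figure is reasonable: section 8 measures spread on completion of the block, before the 30-minute evaluation at which failed blocks are withdrawn, and section 11 retains data already collected.

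2. **Motor weakness.** Label this calculation as secondary, and link it to the 30-minute femoral and sciatic block endpoint if that is what is meant. State both assumed proportions, whether 30% is absolute or relative, the test, and the power at 20 and at 25 per group.

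The cost is a rewritten section, with no added patients or procedures. The sponsor must find an SD and commit to a relevant difference for spread, and the stated power may become less favourable than 80%.
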